Exhaled Carbon Monoxide (CO) Concentrations. We will measure CO exposure using a Micro+ Smokerlyzer® CO monitor for exhaled CO two minutes before lighting the charcoal and 2 minutes at conclusion of each smoking session. CO is a smoke toxicant that reduces the blood's ability to transport oxygen to various organs, including the brain, and can cause dizziness, headache, syncope and nausea. An acute increase in exhaled CO/COHb, and CO poisoning were demonstrated in WP smokers. Post 50 minutes of smoking, mean expired-air CO concentration increased to 32.9 ± 2.7 ppm in WP smokers, and to 7.4 ± 0.5 ppm when smoked cigarettes.

Urinary Biomarkers of Exposure to Waterpipe Tobacco Smoke. Urinary cotinine, NNAL, SPMA, and 1-HOP, will be determined in WP tobacco smokers to assess comparative risk related to WP tobacco smoking across 3 configurations, as shown in Table 1. We expect that this panel of biomarkers will be higher in smokers who add ice cubes in the WP jar; and SPMA and 1-HOP will be lower in smokers who replace charcoal with charcoal-free electric WP head. We will also assess levels of WP smokers' exposure to furan by quantifying its urinary metabolite Furan-BDA-NAL among WP, in which we expect to find an increase post smoking.

Cotinine will be measured as an index of nicotine consumption in WP smokers using emerging WP smoking practices. On average, 70%-80% of nicotine entering the body is converted into its metabolite, cotinine. Daily use of WP tobacco produced a 24-hour mean (95%CI) urinary cotinine level of 785 ng/ml (578-991ng/ml) equivalent to smoking 10

cigarettes/day. Post smoking WP, mean (95% CI) urinary cotinine increased: 11.8 (7.21-19.2) to 55.3 (33.9-90.1) ng/mg creatinine, N=55.

NNAL will be measured as an important tobacco-specific lung carcinogen. In 55 WP smokers NNAL about doubled (2.1-fold) post WP smoking: 1.32 to 2.84 pg/mg creatinine. Higher urinary mean levels (uncorrected) were found in WP smokers in Syria (N=24) [mean (95% CI), 33.0 pg/ml (21.6-50.6 pg/ml)].

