IRB approval, pilot testing of data					
collection					
Refine data collection & procedures					
manual					
Recruitment of participants					
Measures:					
Study Questionnaire, Forms & Diaries					
CO concentrations, Urine samples					
Battelle - Laboratory analyses					
Urine aliquoting, shipping samples to labs					
Data processing-coding, entry, cleaning					
Data analysis and manuscript preparation					
Dissemination of Results (continues beyond year		⁻ 3)			

General Statistical Analysis Strategy. [name] will oversee data processing and. Statistical analyses will be determined by Drs. [name], [name], [name], [name] and [name]. Final analyses will be conducted using SPSS and Stata software by [name], [name], and [name]. Type I error rate will be set at α =.05, and corrections for Type I error will be performed as necessary (e.g., Bonferroni). We will begin with a comprehensive descriptive analysis of levels of toxicants, CO, and urinary biomarkers and their distribution in the various smoking configurations. Arithmetic means and standard deviations, geometric means and 95% confidence intervals, medians and 25th and 75th percentiles, and minimum and maximum levels will be computed for each outcome measure, and for uncorrected and creatinine-corrected values of urinary biomarkers. Correlations between biomarkers will be determined by Pearson's r. Measures will be log-transformed as necessary, to control for skewed distribution, the undue influence of outliers, and violations of assumptions for statistical inference. Dependent or independent samples t-tests, as appropriate, will compare pairs of machine smoking configurations, smokers post-session vs. pre-session, and smokers vs. non-smokers. Missing data from the questionnaire will be handled using multiple imputation in Stata.

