Aim 1 calls for comparing pre/post session change in exhaled CO, and in urinary levels of cotinine, NNAL, SPMA, and 1-HOP in first morning urine samples the morning of, and the morning after, each of 3 WP smoking sessions at home: (Session 1) using charcoal to heat the tobacco and only water in the jar; (Session 2) using charcoal to heat the tobacco and adding ice cubes in the jar; and (Session 3) using electrically heated tobacco and only water in the jar. Among smokers, differences in pre/post change on CO and each biomarker between sessions 1 & 2, and between sessions 1 & 3, will be assessed by mixed regression models to handle repeated measures on each participant. Demographics, duration of smoking, and possible confounding factors, such as number of smokers inside the home and years smoked, will be included as covariates.

Power analysis. As no data exist on effect sizes of differences between session configurations for Aim 2, in Table 4 we show estimated power to detect difference for a range of potential intra-class correlations (ICC) and an effect size of .40 (medium by Cohen's criteria), based on paired z-test, n=50, two-sided alpha=.05. Estimates are conservative, since addition of covariates and adjustment for pre-session CO or urinary biomarker levels in the analyses will increase power.

Table 4. Power				
estimate	es			
Effect	ICC	Darran		
Size	icc	Power		
0.40	0.25	0.637		
0.40	0.50	0.807		
0.40	0.75	0.979		

Aim 2 will examine levels of urinary Furan-BDA-NAL following the analysis strategy described in Aim 1, but using data only from Session 1, the configuration commonly practiced in naturalistic settings, using charcoal to heat the tobacco, and room temperature water in the jar. We will begin with a comprehensive descriptive analysis of demographics and Furan-BDA-NAL levels and their distribution in WP smoker participants. As in Aim 1, analyses will identify differences in metabolite levels between smokers vs. non-smokers, and between pre vs. post WP smoking Session 1, for the sample overall as well as by demographic categories (age, gender, BMI). Pearson's correlations will be conducted between urinary levels of Furan-BDA-NAL and values of other metabolites (cotinine, NNAL, SPMA, and 1-HOP) quantified for WP smoking Session 1.

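### Where the team would apply Bonferroni to the Aim 1 contrasts, Holm's step-down procedure gives the same family-wise control and is never less powerful: a gain of about 2 to 4 points per real contrast in one family of 10, if the six predicted effects are the real ones

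*Combined protocol and SAP*

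**What the plan says.** The General Statistical Analysis Strategy states "Type I error rate will be set at α =.05" and continues "corrections for Type I error will be performed as necessary (e.g., Bonferroni". No other correction is named. The plan does not say what makes a correction necessary, which tests form a family, or how many tests the family holds.

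Aim 1 has five outcomes: exhaled CO and urinary cotinine, NNAL, SPMA and 1-HOP. It tests "differences in pre/post change on CO and each biomarker between sessions 1 & 2, and between sessions 1 & 3", which is two contrasts per outcome.

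The section on urinary biomarkers of exposure predicts that "this panel of biomarkers will be higher in smokers who add ice cubes in the WP jar". That panel is cotinine, NNAL, SPMA and 1-HOP. The same sentence predicts lower SPMA and 1-HOP with the electric head.

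Table 4 gives power for "an effect size of .40", "for a range of potential intra-class correlations (ICC" of .25, .50 and .75, "based on paired z-test, n=50, two-sided alpha=.05". Its alpha carries no multiplicity adjustment.

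**The concern.** Bonferroni compares every p-value with α/m. Holm compares the smallest with α/m, the next with α/(m−1), and so on, stopping at the first failure. Both hold family-wise error at α whatever the correlation between tests. Every hypothesis that Bonferroni rejects, Holm rejects too, and Holm sometimes rejects more. The advantage grows with the share of hypotheses that are false, because each rejection relaxes the next threshold.

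That matters here because the protocol expects several effects at once: four with ice and two with the electric head. With only 50 smokers, a team that followed its one named example could miss configuration effects that Holm would detect at the same family-wise error level.

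**Working it through.** **Inputs.** Effect size .40, n=50, two-sided alpha .05 and ICC .25, .50 and .75 come from the power analysis and Table 4. That paragraph is labelled for Aim 2, but it describes differences between session configurations, which are the Aim 1 contrasts. The 5 outcomes and 2 contrasts come from Aim 1, and the six predicted effects from the urinary biomarker section. Treating all 5 × 2 = 10 tests as one family is an assumption.

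**Step 1: reproduce Table 4.** For a paired z-test, with the effect size in units of the single-measurement SD, the noncentrality is δ = .40 × √50 / √(2(1 − ICC)) and power is Φ(δ − 1.960).

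- ICC .25: δ = 2.309, power .637
- ICC .50: δ = 2.828, power .807
- ICC .75: δ = 4.000, power .979

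All three agree with Table 4.

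**Step 2: Bonferroni over 10 tests.** The threshold is .05/10 = .005 two-sided, so the critical value is 2.807 and power is Φ(δ − 2.807).

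- ICC .25: Φ(−0.498) = .309
- ICC .50: Φ(0.021) = .509
- ICC .75: Φ(1.193) = .884

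**Step 3: Holm over the same 10 tests.** Holm's power has no simple closed form, so it was simulated with 200,000 to 300,000 multivariate normal draws per setting. The two contrasts within an outcome were correlated .5, because they share Session 1. Correlation between outcomes was varied from 0 to .8 (0 to .6 for the six-effect case). Every real contrast was given an effect of .40. With only the six predicted effects real, and the electric-head effects negative, average power per real contrast was:

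| ICC | Table 4, unadjusted | Bonferroni, m=10 | Holm, m=10 | Gain (points) |
|---|---|---|---|---|
| .25 | .637 | .31 | .33 | 2.1 to 2.3 |
| .50 | .807 | .51 | .55 | 4.4 |
| .75 | .979 | .88 | .92 | 3.4 to 3.6 |

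Holm found at least one real effect that Bonferroni missed in about 12%, 22% and 19% of simulated trials at ICC .25, .50 and .75. Its family-wise error was at most .043 in these settings. Bonferroni never rejected a contrast that Holm did not.

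**Step 4: vary what the plan does not fix.** The gain from Holm, in points per real contrast across the three ICC values, was:

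| Family | Real contrasts | Gain (points) |
|---|---|---|
| 10 | all 10 | 4.6 to 11.8 |
| 10 | 5 | 1.8 to 3.3 |
| 10 | 1 or 2 | 0.0 to 0.7 |
| 5 | all 5 | 3.5 to 11.6 |
| 2 (per outcome) | both | 1.2 to 6.2 |
| 2 (per outcome) | one | 0.0 to 0.3 |

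In a family of 10, the largest gains occur at ICC .50 with all 10 contrasts real. Family-wise error under Holm stayed at or below about .05 throughout.

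**The case against.** The strongest reply is that the plan has not chosen Bonferroni. It offers the method as an example, to be used when needed, and Holm already fits that wording. This stands. A reader might infer that the trial has already given up power, or has committed itself to a weaker test. The text supports neither.

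A reader might also take a gain of up to 12 points as the expected benefit. The protocol's own predictions do not lead there. They cover six of the 10 contrasts. The sentence that makes them predicts nothing for CO in either contrast, or for cotinine and NNAL with the electric head. The power analysis also says that no data exist on the size of these effects, so an equal .40 on every real contrast is itself an assumption.

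Thirdly, Bonferroni is valid and has an advantage that Holm lacks: simple simultaneous confidence intervals that agree with the tests. Unadjusted intervals beside Holm-adjusted p-values can exclude zero where the adjusted test is not significant. This too stands, as a cost of the change.

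Lastly, the larger gap in the same sentence is that neither the family nor the trigger for correction is defined. At ICC .50, moving from no adjustment to Bonferroni takes power from .807 to .721 in a family of 2, and to .509 in a family of 10. Those drops exceed what Holm recovers when only the six predicted effects are real. Requiring correction over all 10 tests is a separate and debatable decision, and the case for Holm does not depend on it.

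None of this touches the central fact: for any family the team might choose, Holm costs no power and no error control relative to Bonferroni.

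**Conclusion.** The point holds as an efficiency improvement of modest size. Under one family of 10, Table 4's inputs and only the six predicted effects real, naming Holm gains about 2 points per real contrast at ICC .25, about 4 at ICC .50 and about 3.5 at ICC .75. The size rests on the assumed family, an equal effect of .40 on each real contrast, normally distributed test statistics, complete data on 50 smokers and no gain from covariates. The plan expects covariates to raise power, which would change the figures. The ordering of the two methods rests on none of these assumptions.

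Holm is no remedy for the gap between Table 4 and a multiplicity-adjusted analysis. At ICC .50 it reaches .55 with six real effects, against .807 in the table. Nothing in the plan is invalid because Bonferroni is given as an example.

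**What to change.** In the General Statistical Analysis Strategy, for the Aim 1 contrasts, replace the parenthetical example of Bonferroni with Holm's step-down procedure, applied over whatever family the team defines. Possible wording: *Where the Aim 1 session contrasts are corrected for multiplicity, Holm's step-down procedure will be used at family-wise two-sided .05 over the stated family.* The team should state that family in the same place, but its choice is independent of this change.

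The change is one sentence, needs no new data, and the adjusted p-values can be computed by hand from the ordered unadjusted ones. The price is in reporting: simultaneous intervals are less simple than with Bonferroni. If unadjusted intervals are shown beside Holm-adjusted p-values, label them as unadjusted.

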 - o R01 DA Screen form
 - o RO1 DA Tobacco Smoking Session Day and Exposure form 4.14.16
 - o R01 DA 7 Day Self-Report 4.14.16
 - 11 R01 Appendix K. Saliva Test Procedure [name] 1.3.13

Graduate and Research Affairs

Division of Research Affairs San Diego State University [name] Phone: [name]

Sincerely,

[name]

Chair, Institutional Review Board

A research project to determine the differential effects of waterpipe (WP) smoking practices on biomarkers of toxicants and carcinogens related to waterpipe tobacco smoking in naturalistic settings – urine analyses by Drs. [name] and [name] laboratories. (Table 1)

We will compare exhaled CO, and urinary levels of cotinine, NNAL, SPMA, and 1-HOP in first void WP smoker urine samples the morning of, and the morning after a WP smoking session across 3 configurations, as shown in Table 1

Study Design and Target Population

We will employ a repeated measures design. We will recruit a sample of 50 adult male and female exclusive WP smokers and a control sample of 25 male and female non-smokers. Participants will be recruited via intercept interviews from San Diego County, CA communities. Over a 4-week study period, WP smokers will smoke one WP tobacco head (10g) of *Starbuzz* during 3 separate sessions with a 7-day washout period before each session in their

Table 1. Three waterpipe (WP) smoking sessions.				
3 WP smoking Confiurations at home	Heat Source	WP Jar Contents		
WP smoking session 1	Charcoal ²	Water 4		
WP smoking session 2	Charcoal	Ice cubes 5		
Training for session 3 ¹	Electric ³	Water		
WP smoking session 3	Electric	Water		

- ¹ Smokers will be trained on using the Electric WP head
- ² Quick-light charcoal *Three Kings* (40mm)
- ³ Charcoal-free electrically heated WP head
- ⁴ Room temperature drinking water in the WP jar
- ⁵ Adding ice cubes in the water in the WP jar For all 3 configurations, flavored WP tobacco, *Starbuzz* (10g), Double Apple flavor will be smoked at home, Aluminum sheet (9x9cm) will be used to cover the WP head, volume of water & ice cubes will be standardized.

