home in a naturalistic setting: Week 1-Session 1, WP smokers will smoke using 1 quick-light charcoal and room temperature water in the WP jar, Week 2-Session 2, WP smokers will smoke using 1 quick-light charcoal but adding ice cubes to the water in the WP jar, Week 3-Training for session 3, RAs will train participants on how to use a charcoal-free electrically heated WP head to heat the tobacco, and Week 4-Session 3, WP smokers will smoke WP tobacco without charcoal using the electric WP head and room temperature water. We will collect a) Tobacco Use History; b) 4-week Tobacco Use and Exposure Diaries; c) WP Smoking Session Day and Exposure Form; d) CO exposure: Micro+Smokerlyzer® CO monitor will be used for exhaled CO two minutes pre and post each smoking session; and e) 6 first morning urine samples: pre and post the 3 sessions to measure urinary cotinine, NNAL, 1-HOP, and SPMA. We will measure urinary Furan-BDA-NAL in WP smokers who smoke WP tobacco as commonly practiced using quick-light charcoal and room temperature water in the WP jar (urine samples from Session1).

Inclusion Criteria for Participants

Adult waterpipe smoker: A male or female, 18 years or older, who smokes WP tobacco exclusively, smokes at least 1 WP head per month, and smokes at least 1 WP head per WP smoking session, smokes WP at home, agrees to smoke *Starbuzz* WP tobacco, and lives in a 'smoker home'. Adult non-smoker: A male or female, 18 years or older, who lives in a 'non-smoker home'.

Inclusion Criteria for Homes

A Smoker Home: is a home in which residents have smoked WP tobacco exclusively indoors/outdoors at least in the last month. A Non-smoker Home: is a home where to the knowledge of the residents no smokers have lived in and no visitors had smoked indoors/outdoors in the past month, and where a potential nonsmoker participant who has not been exposed to any secondhand smoke at least in the last month resided full-time.

Exclusion Criteria

Adults with major physical/psychiatric illnesses that are judged by the research assistants (RAs) to interfere with ability to give informed consent or to successfully complete an interview will not be included in the study. Daily WP smokers will be excluded because they may not be able to adhere to the wash-out periods before the 3 WP sessions. Pregnant women are also excluded.

Screening Potential Participants

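### The smokers v non-smokers contrast is non-randomised and unmatched, yet the only test named for it is an unadjusted t-test, and Aim 2's pointer to Aim 1 supplies no other model.

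*Combined protocol and SAP*

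**What the plan says.** Study Design and Target Population sets the group sizes: "We will recruit a sample of 50 adult male and female exclusive WP smokers and a control sample of 25 male and female non-smokers". Both groups come from community intercept interviews. No matching is described, and Gender Representation promises only an effort towards equal numbers of men and women.

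The General Statistical Analysis Strategy names the test: t-tests, paired or unpaired according to the contrast, for comparisons that include "smokers post-session vs. pre-session, and smokers vs. non-smokers". It lists no covariates, weights or matching for the group contrast.

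Aim 2 (Furan-BDA-NAL, Session 1 data only) says: "As in Aim 1, analyses will identify differences in metabolite levels between smokers vs. non-smokers". It adds a breakdown by age, gender and BMI category.

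The Aim 1 paragraph contains no such comparison. Its mixed model is for "Among smokers, differences in pre/post change on CO and each biomarker between sessions 1 & 2, and between sessions 1 & 3". Its covariates are given as: "Demographics, duration of smoking, and possible confounding factors, such as number of smokers inside the home and years smoked, will be included as covariates".

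Inclusion Criteria for Homes states that a non-smoker home "is a home where to the knowledge of the residents no smokers have lived in".

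**The concern.** An analyst following Aim 2 back to Aim 1 finds a smokers-only, between-session model. Two courses are then open on the text as written.

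- **Use the t-test.** The group difference then carries any systematic difference in age, gender or BMI between the two intercept samples. The plan itself treats these three variables as relevant by breaking results down by them.
- **Carry over the Aim 1 model whole.** Some of its covariates describe smoking itself. A control has no session to time, and the number of smokers in a non-smoker home is zero by eligibility. With these in the model, the group coefficient refers to a smoker with none of that exposure, which is not the difference Aim 2 asks about.

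The estimate at stake is the smoker v non-smoker difference, chiefly for Furan-BDA-NAL. The plan says it will be the first to measure this in waterpipe smokers.

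**Working it through.** **1. The plan's own figure.** Table 4 gives power for the paired session contrast, with n = 50, effect size 0.40 and two-sided alpha .05. Power = Φ(0.40·√50 / √(2(1 − ICC)) − 1.96).

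| ICC | Computed | Table 4 |
|---|---|---|
| 0.25 | Φ(2.309 − 1.96) = 0.637 | 0.637 |
| 0.50 | Φ(2.828 − 1.96) = 0.807 | 0.807 |
| 0.75 | Φ(4.000 − 1.96) = 0.979 | 0.979 |

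Table 4 reproduces, but it does not cover the group contrast, and no power is given for that.

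**2. Precision of the group contrast.** In SD units of the log metabolite, SE = √(1/50 + 1/25) = 0.245. The difference detectable with 80% power is (1.96 + 0.842) × 0.245 = 0.69 SD. Power at 0.40 SD is 0.372.

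**3. Effect of a systematic imbalance (assumed values).** The documents give neither an imbalance nor a covariate effect. Assume a trait worth 0.8 SD whose prevalence differs systematically by 20 to 30 percentage points. The bias is 0.8 × 0.20 = 0.16 SD to 0.8 × 0.30 = 0.24 SD. With no true difference, the rejection rate is P(|Z + b/0.245| > 1.96):

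- b = 0.16: shift 0.653, rate 0.0956 + 0.0045 = 10.0%.
- b = 0.24: shift 0.980, rate 0.1635 + 0.0016 = 16.5%.

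A wider grid used a continuous covariate with imbalance 0.25 to 1.0 SD and correlation 0.2 to 0.5 with the outcome. Bias is the product of the two, 0.05 to 0.50 SD, and type I error runs from 5.5% to 52.2% (noncentral t, 73 df). In 10,000 simulated trials per setting, adjusting for that covariate restored the nominal level:

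| Imbalance (SD) | Correlation | t-test | Adjusted |
|---|---|---|---|
| 0.5 | 0.3 | 9.6% | 5.0% |
| 0.5 | 0.5 | 17.2% | 4.9% |
| 1.0 | 0.5 | 52.5% | 5.2% |

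**4. Effect of a covariate that is zero in all controls.** With a proportion p = 50/75 smokers and coefficient of variation CV of the covariate among smokers, the variance inflation of the group term is 1 + (1 − p)/CV².

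- CV 0.25: 1 + 0.333/0.0625 = 6.3.
- CV 0.50: 1 + 0.333/0.25 = 2.3.
- CV 1.0: 1 + 0.333/1 = 1.3.

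The model can be fitted, but its group term changes meaning. A simulation used CV 0.5 and a true mean difference of 1.0 SD, half of it proportional to the covariate. The group coefficient averaged 0.49 (SE 0.39) with the covariate and 1.00 (SE 0.25) without it. The CVs and the half share are assumptions.

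**5. The planned breakdown.** Splitting both groups in half leaves about 12 or 13 controls per category. The SE within a half is √(1/25 + 1/12.5) = 0.346 SD, so the detectable difference is 2.80 × 0.346 = 0.97 SD. The overall contrast stays unadjusted.

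**The case against.** Several points on the other side are sound.

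- **The Aim 1 covariates are not all unusable.** A reader might infer that every one is zero in controls and the model cannot be fitted. The documents do not support that. Demographics come first on the list and vary in both groups. Years smoked is not zero by eligibility, because a non-smoker is defined by the home and recent exposure, and former smokers are not excluded. The model is estimable; the difficulty is interpretation and precision.
- **No text orders smoking-history covariates into a group model.** This stands. Doing so is one reading of Aim 2's reference to the Aim 1 strategy, not an instruction.
- **The plan looks at age, gender and BMI.** It does, but as step 5 shows, this is partial control with small cells.
- **Chance imbalance is already inside the t-test's 5%.** This is correct. Only a systematic difference between the groups inflates the error, and the documents neither show nor rule one out.
- **The expected difference may dwarf the bias.** The protocol cites sulfoxide 3 ranges of 8.7 to 69 and 1.4 to 6.5 pmol/mg creatinine, which do not overlap. The higher range is from cigarette smokers, and the samples are small (N=5, N=16). Waterpipe smokers also abstain for seven days before the pre-session sample, so that difference from controls could be modest.
- **The furan hypothesis is a rise after smoking.** This is a within-person contrast, which differences between the groups do not confound.

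**Conclusion.** The point holds as a gap in the method for one named contrast. The group comparison is unmatched, 50 v 25, and tested without adjustment. The reference to Aim 1 leads to a model that does not contain it. Carrying the Aim 1 covariates over whole would change what the group term estimates and make it less precise.

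A reader might conclude that the comparison is bound to be either confounded or uninterpretable, or that Aim 2 fails. The documents do not support that: adjusting for demographics alone is available, and the pre/post part of Aim 2 and the Aim 1 session contrasts are untouched.

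The size of any confounding cannot be found from the documents. The figure of about 10% to 17% type I error is an illustration under assumed systematic biases of 0.16 to 0.24 SD. The plan also leaves open which smoker sample is set against the controls, and how the controls' two samples are used.

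**What to change.** Replace the smokers v non-smokers t-test with a regression of the log metabolite on group, age (continuous), gender and BMI (continuous).

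- Fit it separately for the smokers' Session 1 pre-session and post-session samples.
- Use both control samples, either through a participant random effect or as the mean of the two log values.
- State that duration of smoking, years smoked and number of smokers in the home enter smoker-only models and not this one.
- Correct the cross-reference in Aim 2 so that it points to this model.
- State that dietary and other non-tobacco furan sources remain uncontrolled. The protocol names processed food, pollution and car exhaust, and the forms it describes include no dietary measure.

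Age, gender, height and weight are already collected on the Tobacco Use History Questionnaire. The cost is wording, one more model per metabolite and time point, and about three degrees of freedom (from 75 − 2 = 73 to 75 − 5 = 70).

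### Table 4 is correct for one uncorrected test, but calling it conservative is not shown to hold once the 10 Aim 1 contrasts are corrected for multiplicity

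*Combined protocol and SAP*

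**What the plan says.** The Power analysis paragraph considers a standardised effect of .40 at three intra-class correlations. It gives the basis of Table 4, and its view of the result, as "based on paired z-test, n=50, two-sided alpha=.05. Estimates are conservative, since addition of covariates and adjustment for pre-session CO or urinary biomarker levels" will add power. It gives no size for that gain.

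Aim 1 covers five outcomes: exhaled CO and urinary cotinine, NNAL, SPMA and 1-HOP. For each it will assess "differences in pre/post change on CO and each biomarker between sessions 1 & 2, and between sessions 1 & 3" in mixed regression models. On covariates it says: "Demographics, duration of smoking, and possible confounding factors, such as number of smokers inside the home and years smoked, will be included as covariates". The pre-session level is not named there.

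General Statistical Analysis Strategy sets alpha at .05 and adds that "corrections for Type I error will be performed as necessary (e.g., Bonferroni"). It names no family of tests and no primary outcome. The power paragraph does not mention multiplicity.

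The power paragraph attaches its calculation to another aim: "As no data exist on effect sizes of differences between session configurations for Aim 2". Aim 2 uses Session 1 data only and has no between-session contrast, so the calculation is read here as belonging to Aim 1.

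**The concern.** Two features of the planned analysis move power away from Table 4, in opposite directions. Adjustment can raise it, and correction for multiple tests lowers it. The paragraph counts only the first and then describes the table as conservative, which a reader will take to mean that true power is at least as high as stated.

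This matters most at ICC .50, where the table only just passes 80%. If the ice or electric-head contrasts come out null, a reader who believes that power was at least .807 may take the null result as stronger evidence than it is. With the family left open, its size could also be settled after the results are known.

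**Working it through.** **Inputs.** n = 50, effect .40, two-sided alpha .05 and ICC r = .25, .50, .75 come from the Power analysis paragraph. The 5 outcomes and 2 contrasts come from Aim 1. Bonferroni is the example in General Statistical Analysis Strategy.

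**Reproducing Table 4.** With effect .40 in SD units, the paired difference has SD √(2(1−r)), so the standardised shift is L = .40 × √50 / √(2(1−r)). This gives L = 2.309, 2.828 and 4.000. Power is Φ(L − 1.960):
- r = .25: Φ(0.349) = .637
- r = .50: Φ(0.868) = .807
- r = .75: Φ(2.040) = .979

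All three match, so Table 4 contains no arithmetic error.

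**Possible families.** Three sizes can be read from the text:
- m = 2: the two contrasts within one outcome.
- m = 6: the directional expectations in the urinary biomarkers section, "this panel of biomarkers will be higher in smokers who add ice cubes in the WP jar; and SPMA and 1-HOP will be lower" with the electric head. That is 4 biomarkers for ice plus 2 for electric heating.
- m = 10: all 5 × 2 contrasts.

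**Bonferroni power, before any adjustment gain.** Replace 1.960 by z(1 − .05/(2m)), which is 2.241, 2.638 and 2.807 for m = 2, 6 and 10.

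| Tests | Alpha per test | ICC .25 | ICC .50 | ICC .75 |
|---|---|---|---|---|
| 1 (Table 4) | .05 | .637 | .807 | .979 |
| 2 | .025 | .527 | .721 | .961 |
| 6 | .0083 | .371 | .575 | .913 |
| 10 | .005 | .309 | .509 | .884 |

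For example, at ICC .50 with 10 tests: Φ(2.828 − 2.807) = Φ(0.021) = .509.

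**Gain needed to restore Table 4.** If adjustment leaves a fraction f of the variance of the paired difference, L becomes L/√f. Setting L/√f − z(m) = L − 1.960 gives f = (L / (L − 1.960 + z(m)))². At ICC .50 with 10 tests, f = (2.828/3.675)² = .592, so 40.8% must be removed.

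| Tests | ICC .25 | ICC .50 | ICC .75 |
|---|---|---|---|
| 2 | 20.5% | 17.3% | 12.7% |
| 10 | 46.5% | 40.8% | 31.9% |

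The documents give no variance reduction, R² or pre/post correlation to set against these figures.

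**If no correction is made.** Table 4 stands and any gain makes it conservative. Ten tests at .05 then carry a familywise error of 1 − .95¹⁰ = .40 if independent, and at most 10 × .05 = .50 in any case. These outcomes are correlated, so the actual value is probably below .40.

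**The case against.** The strongest reply is that the word conservative is tied, in its own sentence, to covariates and pre-session adjustment at the stated alpha. Read that way it says nothing about multiplicity, and correction is promised only where necessary. This stands as far as it goes: with every contrast tested at .05 the statement can be true. But the plan itself foresees correction and names no primary outcome, so the power of the corrected analysis has to be shown somewhere, and it is not.

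A second reply is that the gain may be large enough. It may. For 2 tests the required reduction is modest. Covariates that stay fixed within a person, such as demographics and years smoked, add essentially nothing as main effects to a within-person contrast. Duration of smoking, if it means session length, is recorded at each session and could contribute. The pre-session level could contribute more. None of this is quantified.

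A reader might go further and infer that the gain suffices only if pre- and post-session levels are highly correlated. The documents do not support that. They do not say whether the .40 and the ICC describe post-session levels or pre/post change, and Aim 1 analyses change. Let ρ be the correlation between the session differences in pre and in post level. On the level reading, adjustment removes ρ² of the variance, so the gain rises with the size of ρ. On the change reading, with equal variances assumed, it removes (1−ρ)/2, so the gain falls as ρ rises. Break-even at ICC .50 is then ρ of at most 1 − 2 × .408 = .18 for 10 tests and 1 − 2 × .173 = .65 for 2.

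That Aim 1 does not list the pre-session level is a difference of detail, since its covariate list is open-ended. The Aim 2 label is clerical.

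**Conclusion.** The point holds in a limited form. Table 4 is right for what it computes. The statement that it is conservative is not shown to hold once any correction is applied, because an unquantified gain is counted and a calculable loss is omitted. At ICC .50 the loss alone takes .807 to .721 for 2 tests or .509 for 10.

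A reader might infer that the claim is false, or that the trial's real power is about one half. Neither follows. The corrected figures come before any adjustment gain, they use single-step Bonferroni, and the 10-test figure assumes that all contrasts form one family.

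The figures take the plan's own effect, ICC range and z-approximation, with all 50 smokers contributing to each contrast. The required variance reductions depend on no assumption about the pre/post correlation. The statement should be corrected before analysis; the design need not change.

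**What to change.** 1. Fix the Aim 1 correction family before analysis. The choice is the sponsor's: 2 contrasts per outcome, the 6 directional urinary expectations, and all 10 are the natural candidates. Restate Table 4 at the matching alpha (.025, .0083 or .005), labelled as single-step Bonferroni before covariate adjustment.
2. Replace the sentence calling the estimates conservative with: *Power is shown before covariate adjustment; the size of any gain is not known.*
3. Use Holm in place of Bonferroni. It gives the same familywise control and rejects everything that Bonferroni rejects, so the restated table remains a floor for it.
4. Name the pre-session level in the Aim 1 model, so that it agrees with the power paragraph, and split it into the person's mean and the within-person deviation. A single common slope mixes between- and within-person relations and can lose precision on the session contrast. As an illustration, assume ICC .75 for levels, all cross-session correlations equal to it, a same-session pre/post correlation of .839 and three sessions. The within-person slope is (.839 − .75)/.25 = .356, but a random-intercept model with one slope fits about .82. The residual fraction is then 1 − 2(.82)(.356) + .82² ≈ 1.09, a loss.
5. Minor: change Aim 2 to Aim 1 in the power paragraph.

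The cost is wording and a recomputed table, with no added participants, visits or samples. The stated power becomes less favourable.
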